8.3.2 Secondary Endpoints

Part A

- PK parameters for M5717.

Part B (optional)

- PK parameters for M5717.

Part C

- PCT, MIC, PCT $\frac{1}{2}$, MPC, lag phase, number of subjects with recrudescence
- Malaria Clinical Score
- Nature, incidence, and severity of AEs/SAEs, including relationship to trial treatment, AEs/SAEs leading to dose modification or discontinuation of trial treatment
- Incidence of clinically significant changes and abnormalities in safety laboratory parameters (hematology, coagulation, biochemistry [specifically ALT and AST], and urinalysis)
- Incidence of clinically significant changes and abnormalities in vital signs (body temperature, BP, and heart rate), respiratory rate, and 12-lead ECG.

CCI

8.4 Analysis Sets

For purposes of analysis, the following populations are defined:

Table 13 Definition of Statistical Analysis Populations

Population	Description
Enrolled	The Enrolled Analysis Set will include all subjects who provided signed informed consent, regardless of treatment status in the trial. This set will be used for subject disposition.
Safety	The Safety Analysis Set will include all subjects who receive at least one dose of investigational medicinal product (M5717 or placebo for Part A and Part B; M5717 for Part C). Subjects will be analyzed according to the actual treatment they receive.
Pharmacokinetic	The Pharmacokinetic Analysis Set will consist of all subjects who receive at least one dose of M5717, have no clinically important protocol deviations or important events affecting pharmacokinetics, and provide at least one (measurable) postdose concentration. Subjects will be analyzed according to the actual treatment they receive. All pharmacokinetic analyses will be based on this analysis set. Subjects who receive placebo will not be part of the Pharmacokinetic Analysis Set.
Pharmacodynamic	The Pharmacodynamic Analysis Set will be defined for the Part C only. The Pharmacodynamic Analysis Set will include all subjects who receive at least one dose of M5717 in Part C without clinically important protocol deviations or important events affecting pharmacodynamics. Subjects in the Pharmacodynamic Analysis Set must have evaluable pharmacodynamic data. All pharmacodynamic analyses will be based on this analysis set.

8.5 Description of Statistical Analyses

8.5.1 General Considerations

The results of this trial will be reported using summary tables, figures, and data listings, as appropriate. All data will be summarized by trial part, dose level and/or scheduled time point, as appropriate and otherwise specified.

For demographic, baseline and safety assessments, continuous measurements will be summarized by means of descriptive statistics (ie, number and percentage of observations, number and percentage of missing observations, mean, standard deviation, median, 25th and 75th percentiles, minimum, and maximum) and categorical data will be summarized by means of frequency tables (ie, count and percentages), if not stated otherwise.

Given its exploratory nature, no formal statistical hypothesis testing will be performed in this trial. Data will be presented by actual dose or treatment, and subjects receiving placebo will be pooled across dosing cohorts for the purposes of summarizing the safety results (Part A and Part B). Missing data will result in a reduced sample size for that parameter. Since the statistical analyses will be predominantly descriptive presentations in tables and individual data listings, no action will be taken to handle missing data. A subject who withdraws prior to the last planned observation in a trial period will be included in the analyses up to the time of discontinuation.

PK concentrations in blood, and PK and PD parameters will be presented in tables and descriptively summarized by trial part, dose level, trial day, and/or nominal time point, as appropriate, using n, arithmetic mean, standard deviation, median, minimum, maximum, and CV%. Values below the LLOQ will be taken as zero for descriptive statistics of PK concentrations. Descriptive statistics of PK and PD parameters will additionally show the GeoMean, the geometric CV%, and the 95% CI for the GeoMean.

Graphical displays will be given, where appropriate. Details of the statistical analysis will be described in the statistical analysis plan (SAP).

8.5.2 Analysis of Primary Endpoints

8.5.2.1 Safety

Part A and Part B

Safety data analysis will be conducted on the Safety Analysis Set. The number and percentage of subjects experiencing one or more AEs will be summarized by dose level group, relationship to IMP, and severity. AEs will be coded using Medical Dictionary for Regulatory Activities terminology. Laboratory parameters will be summarized using descriptive statistics, by postdose shifts relative to baseline, and data listings of abnormal results as appropriate. Vital signs and ECG data will be summarized for observed and changes-from-baseline values by dose level using descriptive statistics. Clinically noteworthy ECG findings for individual subjects will be listed and summarized as appropriate.

8.5.2.2 Pharmacokinetics

Part C

All PK blood concentrations and PK parameters will be descriptively summarized by trial part, dose level, trial day, and/or nominal time point, as described in Section 8.5.1. For calculation of descriptive statistics of blood concentrations, values below the LLOQ will be set to zero.

The statistical analysis of dose proportionality (and the statistical analysis of linearity and accumulation, if applicable, depending on the trial design of Part C) that is described in Section 8.5.3.1, will be repeated after including applicable PK parameters from Part C.

8.5.2.3 Pharmacodynamics

Part C

The primary PD variable is the PRR of asexual parasites based on qPCR after administration of M5717. Secondary PD variables are PCT, MIC, Pct½, and MPC (calculation to be described in the SAP), clinical score, and the number and percentage of subjects with recrudescence. Statistically, recrudescence is defined as an increase in parasitemia > 1 log₁₀ over 2 or more consecutive qPCR results. To be considered recrudescence this increase must occur after the initial decrease in parasitemia post-IMP administration.

The PRR for asexual parasites will be estimated using the slope of the optimal fit of the log-linear relationship of the parasitemia decay based on the PD Analysis Set. The optimal fit can be derived using summarized replicate parasitemia data, which have been cleaned by dealing with potential outliers, values below the limit of detection and nondetectable values (ND). The optimal fit of the log-linear parasitemia-by-time relationship is determined by using left and right censoring to systematically remove the potential lag phase and tail phase of the parasitemia decay. The decay rate, estimated by the slope coefficient from the log-linear decay regression of qPCR data, will be calculated for each subject. The overall cohort-dose specific PRR will be estimated with its 95% CI by calculating the weighted average slope estimate and corresponding standard error (SE) using an inverse-variance method. Only subjects who have optimal regression models with appropriate fit contribute toward the dose-specific PRR.

For any replicate parasitemia values below LLOQ, the value is substituted with LOQ/2. The LOQ is assumed to be 64 parasites/mL of blood, based on published data (9). For any values that were not detected (ND) the value is set to 1, such that when the data is log₁₀ transformed the ND = log₁₀(1) = 0. If all replicates for a subject within a time point are ND, the first time point with all ND is included in model fitting, and all subsequent time points are set to 'missing', regardless of whether parasitemia values increased afterwards due to potential recrudescence of malaria infection. The data used for all subsequent model selection and fitting calculations is comprised of arithmetic mean of the replicate log₁₀ parasitemia value per time point per subject up to the first time all replicates are ND.

The algorithm to obtain the log-linear decay for each subject is based on the log-linear regression detailed in Equation (1), where Time is the number of hours since administration of antimalarial treatment ($Time = 1, \dots, m$), and β_0 and β_1 are the intercept and slope estimates, respectively.

$$\log_{10} Parasitemia = \beta_0 + \beta_1 Time \quad (1)$$

Based on the cleaned and processed parasitemia data for each subject, the iterative algorithm to determine the optimal log-linear decay for each subject is summarized below. The iterative algorithm is continued until a minimum of 4 observations are available.

The optimal log-linear regression model for a subject is deemed an appropriate fit if the overall model p-value < 0.001.

CCI

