Part C is a single-center, open-label trial using the *P. falciparum* IBSM human challenge to assess the antimalarial activity of M5717 in healthy subjects infected with malaria under controlled conditions. The trial is planned to be conducted in up to 3 cohorts (n=8 per cohort). CCI

The following options may be considered:

[figure not shown]
- If the initial dose leads to a complete reduction of parasitemia and does not lead to observed recrudescence in any subjects, then a lower dose will be used for the second cohort
- If recrudescence is observed in an insufficient number of subjects, so that the MIC cannot be derived, then a second cohort with a lower dose should be initiated
- If recrudescence is observed in enough subjects so that the MIC can be derived, then the need for a higher dose will be evaluated and decided by the SMC.

CCI

Figure 6 presents an illustration of the time schedule for Part C.

Figure 6 Illustration of Time Schedule for Challenge Model

In D1 to In D9 = Day of Inoculum administration (In D1) to 9 days post administration of the Inoculum (In D9); IMP = investigational medicinal product; IV = intravenous.

This example assumes that the IMP is administered on Inoculum Day 9.

In order to be able to observe the MIC and model the MPC, one needs to assess the drug concentration at the time that parasite count is at its lowest level. This implies that the lowest parasite count must be observed. Provided that a high enough dose is administered, the MIC should be reached after the subject has recovered from any clinical symptoms of malaria, and when parasite densities have fallen below the level of microscopic detection, as the sensitivity of microscopy is only 50/ μ L (approximately 10^8 parasites total). Sensitive qPCR methods now allow timely (assay time approximately 4 hours) detection of very low parasitic densities (below 100 parasites/mL, which represents sensitivity up to 1,000 times greater than thick blood smears by microscopy), so it is possible to follow the sub-latent parasitemia levels as they decline and then rise again. Once there is clear evidence by real-time qPCR that parasitemia is rising (parasitemia of $\geq 5,000$ asexual blood stage parasites and increasing 2-fold within 48 hours), rescue medication will be administered at the decision/discretion of the Investigator. The subject will thus be cured of their infection before or at emergence of advanced clinical symptoms of malaria infection.

CCI

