8.1 Sample Size

Given the exploratory nature of this trial, the sample size in Part A and Part B is not based on formal statistical calculations. The sample size is based on experience from previous similar Phase I trials which will provide sufficient safety and tolerability data for M5717 to achieve the objectives from Part A and Part B of the trial while exposing as few subjects as possible to the IMP and procedures.

For Part C, the objective is to define the PK/PD relationship of M5717. Historically, 8 participants in a dose cohort have proven sufficient to characterize the effects of a drug on malaria parasite kinetics following induction in healthy volunteers using inoculation with blood stage *P. falciparum*. Therefore, the sample size of the current trial for *P. falciparum* infection (n=8 per cohort) is comparable with previous trials, and based on previously published experience (3, 10). Two or 3 cohorts should be sufficient to achieve the objective in Part C, which is to define the PRR, the major PD parameter, and to derive the MIC and MPC of the compound.

As the exact number of subjects showing recrudescence is unknown, 3 cohorts are planned to be able to evaluate a higher or lower dose of IMP to collect sufficient data on subjects showing cure as well as recrudescence.

In Part C, subjects who are withdrawn from the trial by the Investigator due to AEs after the start of the inoculum will generally not be replaced. The final decision will be taken after discussion with the Sponsor.

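### The 95% CI for the Part C cohort PRR is pooled by an inverse-variance method with no stated between-subject variance; read as fixed-effect, it is too narrow whenever subjects' slopes differ

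*Protocol*

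**What the plan says.** Protocol 8.3.1 lists PRR as a Part C primary endpoint. Protocol 8.1 treats it as the main pharmacodynamic output: "Two or 3 cohorts should be sufficient to achieve the objective in Part C, which is to define the PRR, the major PD parameter". Section 5.2.4 plans up to three cohorts of eight.

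Protocol 8.5.2.3 then works in two stages.
- Stage one: "The decay rate, estimated by the slope coefficient from the log-linear decay regression of qPCR data, will be calculated for each subject". A search trims the lag and tail phases: "The iterative algorithm is continued until a minimum of 4 observations are available". A subject's model is "deemed an appropriate fit if the overall model p-value < 0.001".
- Stage two: the cohort PRR "will be estimated with its 95% CI by calculating the weighted average slope estimate and corresponding standard error (SE) using an inverse-variance method". Eligibility is restricted: "Only subjects who have optimal regression models with appropriate fit contribute toward the dose-specific PRR".

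Three other places matter. Protocol 8.5.1 plans a geometric mean, geometric CV% and 95% CI for PD parameters generally. The text after the fit rule in 8.5.2.3 is redacted. SAP 16.2.1 moves the PD parameter methods to separate reporting, so the SAP gives no PRR formula.

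**The concern.** A dose-level PRR from eight volunteers has two sources of error: noise in each subject's regression, and real differences in clearance rate between subjects. The usual inverse-variance formula weights each slope by 1/SE² and takes the pooled SE as (Σ 1/SE²)^(-1/2). That counts only the first source. It describes these eight people as if they shared one slope, whereas the result is reported as the PRR of the dose. The weights are also estimated, from as few as four points per subject. In a trial that estimates and does not test, the interval is the main statement of uncertainty about this endpoint.

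**Working it through.** **Figures in the plan.** The documents state no PRR value, slope SD, SE or CI width, so there is nothing to reproduce. The qPCR schedule is redacted. All inputs below other than n = 8, the 95% level, the 4-point minimum and p < 0.001 are assumptions.

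**Step 1: closed form.** Take n subjects with equal per-subject SE s and between-subject slope SD τ. The fixed-effect SE is s/√n. The true SE of the cohort mean is √((τ² + s²)/n). The ratio is k = √(1 + (τ/s)²), and coverage of the nominal 95% CI is 2Φ(1.96/k) − 1.

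| τ/s | k | coverage |
|---|---|---|
| 0 | 1.00 | 95.0% |
| 0.25 | 1.03 | 94.3% |
| 0.5 | 1.12 | 92.0% |
| 1 | 1.41 | 83.4% |
| 2 | 2.24 | 61.9% |
| 3 | 3.16 | 46.5% |

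**Step 2: what the fit rule implies for s.** In a one-slope regression on m points, p < 0.001 means |slope|/SE > t(0.9995, m − 2). The SE entering the pool is therefore capped at 1/t of the slope:
- m = 4: 1/31.6 = 3.2%
- m = 5: 1/12.92 = 7.7%
- m = 6: 1/8.61 = 11.6%
- m = 8: 1/5.96 = 16.8%

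With eight similar subjects, the pooled SE is at most these values divided by √8, or 1.1%, 2.7%, 4.1% and 5.9% of the slope. Modest variation between subjects can therefore match or exceed s.

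**Step 3: simulation with estimated SEs and the fit rule** (20,000 cohorts of 8; mean slope −0.04 log10/h; 8 points at 12, 16, 20, 24, 30, 36, 48 and 60 h; residual SD 0.15 log10). The sum of squares of the times about their mean is 9,476 − 8 × 30.75² = 1,911.5. So s = 0.15/√1,911.5 = 0.0034, and at CV 10% τ/s = 0.004/0.00343 = 1.17. Half-widths are in log10 per 48 h.

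| slope CV | τ/s | fixed-effect: coverage, half-width | t on subject slopes: coverage, half-width |
|---|---|---|---|
| 0% | 0 | 82%, 0.096 | 95%, 0.131 |
| 5% | 0.58 | 76%, 0.097 | 95%, 0.152 |
| 10% | 1.17 | 64%, 0.096 | 95%, 0.201 |
| 20% | 2.33 | 43%, 0.097 | 95%, 0.325 |
| 30% | 3.50 | 31%, 0.098 | 95%, 0.454 |

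Random-effects pooling (DerSimonian-Laird) with a Hartung-Knapp t interval covered 92–95% in these rows. The 82% at zero CV arises because weights from few-df SEs are combined with a normal quantile.

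**Step 4: other settings.**
- Across 8 to 13 samples and residual SD 0.15–0.3, fixed-effect coverage at CV 10–30% was about 20–78%.
- At zero CV it was mostly 82–90%. It was 77% with 8 points, residual SD 0.3 and the fit rule, and 58% with 5 points, residual SD 0.15 and the fit rule.
- Step 3 omits the window search. Adding a lowest-p search over windows of at least 4 points (rule assumed; 9 samples over 48 h, residual SD 0.15) gave about 77% at zero CV and about 40% at CV 20%.

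**Step 5: does a t-interval always repair it?** No. With 8 points and residual SD 0.3, only about 53% of subjects pass the fit rule. The t-interval then covered 90% at zero CV and 89%, 86% and 81% at CV 10%, 20% and 30%. With 9 samples over 48 h and residual SD 0.3 it covered roughly 84–92%, with slopes overstated by 4–16%. The rule favours steep slopes. The fixed-effect CI was worse in every setting.

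**The case against.** The best reply is that the fixed-effect reading is an inference. Random-effects pooling is also an inverse-variance method, part of 8.5.2.3 is redacted, and SAP 16.2.1 defers the method. This stands. A reader might infer that the plan sets between-subject variance to zero. The documents show only that none is visibly specified.

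A reader might also infer that the interval is certain to be far too narrow. Without τ and s this cannot be shown. At τ/s up to about 0.25 the closed-form loss is negligible.

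Protocol 8.5.1 already plans a geometric-mean CI for PD parameters. If it is applied to subject-level PRR and computed in the usual way on logs, it reflects between-subject spread. This helps but does not settle the matter: 8.5.2.3 gives PRR its own interval, and nothing says which of the two prevails.

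Finally, a reader might infer false differences between dose cohorts or a misdirected Phase II dose. Protocol 8.5.1 says "no formal statistical hypothesis testing will be performed in this trial", and no visible text compares cohorts by these intervals. The visible cohort options in 5.2.4 turn on recrudescence and whether MIC can be derived. The same section names MIC and MPC as the aids to identifying a Phase II dose, and SAP 16.2.3 gives PK/PD modelling its own plan.

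**Conclusion.** The point holds conditionally. The visible rule for a primary endpoint's CI includes neither a between-subject variance nor a t reference. On its ordinary reading it understates the uncertainty of a dose-level PRR whenever true slopes differ. The shortfall runs from negligible to severe, depending on τ/s, slope heterogeneity and the number of points. The fit rule makes a small s likely among contributing subjects, which is why modest heterogeneity is enough to matter. The simulated figures rest on assumed sampling times, mean slope, residual SD and slope CV. The consequence is overstated precision in a descriptive summary. Changing the pooling formula removes most of the problem, but not the selection caused by the fit rule.

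**What to change.** In Protocol 8.5.2.3 and the separate PD plan, name the variance model and replace any fixed-effect SE with one of these:
- a linear mixed model of log10 parasitemia with random subject slopes;
- two-stage REML pooling of subject slopes with a Hartung-Knapp t interval;
- the mean of subject slopes with a t(n − 1) interval.

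Report the between-subject SD of the slope beside the cohort PRR. State which interval is primary and how it relates to the geometric-mean CI in 8.5.1. Since log PRR is the slope times a fixed time window, the third option and a log-scale t interval for the geometric mean of subject PRR coincide if the same subjects are used.

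Report by cohort how many subjects fail the p < 0.001 rule, and add a sensitivity estimate that includes them.

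The cost is a few sentences, a little more analysis work and a wider interval. No new data are needed.

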8.5.3 Analysis of Secondary Endpoints

8.5.3.1 Pharmacokinetics

Part A and Part B

All PK blood concentrations and PK parameters will be descriptively summarized by trial part, dose level, trial day, and/or nominal time point, as described in Section 8.5.1. For calculation of descriptive statistics of blood concentrations, values below the lower limit of quantitation of the assay (LLOQ) will be set to zero. CCI

CCI

CCI

CCI

8.5.3.2 Other Secondary Endpoints

Part C

All secondary PD variables, including PCT, MIC, Pct $\frac{1}{2}$, MPC, lag phase, and clinical score, will be descriptively summarized. Further details will be provided in the SAP as well as for the number and percentage of subjects with recrudescence. PCT and MIC are defined in [Table 10](#). The MIC is the drug concentration at which the relative rate of change in parasitemia is equal to zero (see [Figure 5](#)). In other words, the MIC is the drug concentration at which the rate of parasite killing is equal to the rate of parasite reproduction and represents a “steady state”. Implicit in this definition is the assumption that the MIC value is invariant of the dose administered.

Safety data will be similarly analyzed as described for the safety analysis in Part A and Part B in [Section 8.5.2](#).

CCI

CCI

8.6 Interim and Additional Planned Analyses

No formal interim statistical analysis is planned. However, to support timely decision-making, the Sponsor may decide to perform a final analysis of a trial part after the completion of a trial part. The data for that trial part will be locked and unblinded as described in Section 6.10.

An SMC will be established according to the SMC charter. Membership, mandate, and processes of the SMC will be detailed in the SMC Charter. Information regarding the SMC decision criteria are provided in Section 5.2.8.

9 Ethical and Regulatory Aspects

9.1 Responsibilities of the Investigator

The Investigator is responsible for the conduct of the trial at the site and will ensure that the trial is performed in accordance with this protocol, the ethical principles outlined in the Declaration of Helsinki, the Notes for Guidance on GCP (CPMP/ICH/135/95), as adopted by the Australian Therapeutic Goods Administration (2000) (NHMRC National Statement on Ethical Conduct in Human Research), and any other applicable regulations. The Investigator must ensure that only subjects who have given informed consent are included in the trial.

9.2 Subject Information and Informed Consent

An unconditional prerequisite for each subject prior to participation in the trial is written informed consent, which must be given before any trial-related activities are carried out. Adequate information must therefore be given to the subject by the Investigator or an appropriate designee (if local regulations permit) before informed consent is obtained.

A subject information sheet must be prepared in the local language in accordance with ICH GCP and provided to the subject for the purpose of obtaining informed consent. In addition to providing this written information to a potential subject, the Investigator or a designee will inform the subject verbally of all pertinent aspects of the trial, using language chosen so that the information can be fully and readily understood by laypersons. The subject will be given sufficient time to read the information and the opportunity to ask questions and to request additional information and clarification.

If permitted by national regulations, a person other than the Investigator may inform the subject about the trial and sign the PICF, as above.

After the information is provided by the Investigator, the PICF must be signed and personally dated by the subject and the Investigator.

The signed and dated declaration of informed consent will remain at the Investigator's site, and must be safely archived by the Investigator/designee so that the forms can be retrieved at any time for monitoring, auditing and inspection purposes. A copy of the signed and dated PICF should be provided to the subject prior to participation.

Whenever important new information becomes available that may be relevant to the subject's consent, the written subject information sheet and any other written information to be provided to the subjects will be revised by the Sponsors/designees and be submitted again to the PPD HREC for review and favorable opinion. The Investigator/designee will explain the changes to the previous version to each trial subject the agreed, revised information will be provided to each subject in the trial for signing and dating.

